8.1.5.2 IGA Missing Data Imputation

A similar procedure will be used for the analyses based on proportion of IGA successes wherein the ANCOVA analysis is replaced with a logistic regression analysis. Specifically, missing IGA values from which the dichotomized IGA is derived will be estimated by MCMC.

The pattern of missing observations in each treatment group cannot influence the missing value estimation in the other because the imputation is being conducted independently for each treatment group.

The missing IGA values will be derived for the analysis using the method of MCMC multiple imputation. Multiple imputation and subsequent analysis will involve 3 principal tasks:

1. Create a data set, one for each treatment group, of patients with observed values and those needing estimation by MCMC. The missing IGA values in each data set will be filled in using the MCMC method 5 times to generate 5 data sets. The resulting data sets for each treatment arm will be combined into one complete data set by imputation.

Syntax:

```
proc mi data=datain out=dataout seed=&seed. nimpute=5 <options>;  
  where trtpn=(1, or 2);  
  mcmc chain=multiple;  
  var baseline week2 week4 week8 week12;  
run;
```

2. For each complete data set, the dichotomous success rate (clear or almost clear) will be computed. The estimated global values will be rounded to the nearest integer value prior to evaluating the success rate. Each complete data set will be analyzed with a logistic regression with factors of treatment group and analysis center.
3. The results from these analyses will be combined into a single inference using SAS PROC MIANALYZE.

A total of 2 random seeds will be needed to impute IGA for the two treatment groups. Those 2 random seeds have been pre-specified by using a random number generator:

- IGA Week S5G4T-1: Seed = 712066910
- IGA Week Vehicle: Seed = 1200150465

8.1.5.3 Medication Date Imputation

If the medication start date is incomplete, then it will be imputed as follows for the purpose of determining concomitant use:

- If the start date is completely missing, the start date will be equal to the first dose date. However, if the stop date is not missing and is before the first dose date, then the stop date will be used instead.
- If the start day is missing, the first day of the month will be used.

- If the start day and month are missing, then the first day of the first month (January) will be used.

If the medication stop date is incomplete, then it will be imputed as follows for the purpose of determining concomitant use:

- If the stop date is completely missing and the medication is not ongoing, the stop date will be equal to the last dose date or date of completion/withdrawal, whichever is the latest.
- If the stop day is missing, the last day of the month will be used.

If the stop day and month are missing, then the last day of the last month (December) will be used.

8.1.6 Interim Analyses and Data Monitoring

No interim analysis or data monitoring is planned for this study.

8.1.7 Multicenter Studies

The clinical study will be conducted under a common protocol for each investigational site with the intention of pooling the data for analysis. Every effort will be made to promote consistency in study execution at each investigational site. The study is intended to be conducted in a manner such that a minimum of 15 subjects will be randomized and included in the ITT population (i.e., at least ten subjects in the active treatment arm and five subjects in the vehicle treatment arm) for any investigator. In the event that there are too few subjects in a treatment arm for an investigational site, then the site's data will be combined with other site's data to achieve the desired sample size minimum per treatment arm. The combining of investigator data will be accomplished by taking the data of the investigator with the smallest enrollment and combining them with the data of the investigator with the largest enrollment, restricted to investigational sites which did not meet minimum enrollment. If there is a further need to combine data, then the data of the investigator with the second smallest enrollment will be combined with the site's data which had the second largest enrollment (restricted to investigational sites which did not meet minimum enrollment), and so on. This process will continue for all investigators who did not have a minimum of 15 subjects enrolled. The process of combining investigator data that have insufficient subjects per treatment arm will result in redefining the groups of investigators for the purposes of statistical analyses. These combined groups will be referred to as "analysis centers" in the statistical analyses.

The consistency of treatment response will be investigated across the analysis centers subsequent to combining the data as described above. Statistical tests will be conducted to identify if there are extreme analysis centers that could affect the interpretation of common statistical and clinical conclusions. An analysis center by treatment interaction will be included in the primary analyses to test for parallel treatment effect at an alpha level of 0.10. Change from Baseline in inflammatory lesions will be analyzed with an ANCOVA (unranked or ranked) with factors of treatment group, analysis center, and treatment group by analysis center interaction, and the Baseline lesion count variable as a covariate. For the purpose of testing consistency of treatment response, the dichotomized IGA will be analyzed with a logistic regression with factors of treatment group, analysis center, and the interaction term of treatment group by analysis center. Further examination will follow for any variables that have a significant ANCOVA or logistic regression interaction term.

In the event that the ANCOVA or logistic regression interaction (referred to henceforth as the “appropriate test”) p-value is less than or equal to 0.10, a sensitivity analysis that excludes analysis centers with the extreme efficacy result will be performed to determine the robustness of the treatment effect. On the other hand, if all three analyses result in interaction terms with p-values greater than 0.10, then the conclusions from the pooled data will be considered to be free of the impact of extreme analysis centers.

The first step in conducting a sensitivity analysis is to identify the extreme analysis center or centers that contribute to the statistical significance of the appropriate test. The process involves submitting subsets of analysis centers to the appropriate test and observing the appropriate test p-value for the subset. Subsets with p-values greater than 0.10 for the appropriate test are considered homogeneous.

The search for an extreme analysis center begins by analyzing all subsets that can be created by excluding one analysis center. If one or more of the subsets result in an appropriate test p-value greater than or equal to 0.10, then the analysis center excluded from the subset with the largest p-values for the appropriate test is deemed to be the extreme analysis center.

If all appropriate test subset p-values are less than or equal to 0.10, then the process will analyze the appropriate test for all subsets that can be created by excluding two analysis centers. If one or more of these subsets generate appropriate test p-values larger than 0.10, then the analysis centers excluded from the subset with the largest appropriate test p-value are deemed the extreme analysis centers.

Thus, the process of identifying the extreme analysis centers will continue in a stepwise manner by first excluding one, then two, then three, etc., analysis centers until the appropriate test p-value exceeds 0.10.

Once the extreme analysis center or centers have been identified, then the treatment p-values of the remaining analysis centers will be computed. Inferences will be drawn from the p-values as well as any pertinent observations regarding the extreme analysis center or centers. Additionally, it is noted that this process excludes patients from the analysis in a non-random manner and has an unpredictable impact on the power of the treatment effect test. In the event that the treatment effect of the remaining subset is not statistically significant, due consideration of the post-hoc aspects of the process will be given when the results are interpreted. Conclusions will be presented by the Sponsor as appropriate to the findings of the sensitivity analysis.

Prior to investigating the treatment effect within the analysis centers, the treatment effect within investigational site will be investigated to determine if the site-to-site variability is such that it could mask the analysis center effects. Thus, prior to pooling, change from Baseline in inflammatory lesions will be analyzed with an ANCOVA (unranked or ranked) with factors of treatment group, investigational site, and treatment group by investigational site interaction, and the Baseline lesion count variable as a covariate. The dichotomized primary endpoint will be analyzed with a logistic regression with factors of treatment group, investigational site, and the interaction term of treatment group by investigational site. If any of the analyses are not computationally feasible due to some investigational sites having very few subjects enrolled, the low-enrolling investigational sites will be excluded from the analysis.

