9. DETERMINATION OF SAMPLE SIZE

The following power calculations are based on the observed Week 12 results of the Phase 2 study, SGT-EBP01-09. This study was a three-arm trial including E-BPO cream, 1% and 5%, and vehicle in the treatment of rosacea. Estimates from the E-BPO cream, 5% arm were used in the power assessments. The anticipated randomization ratio is 2:1 for E-BPO cream, 5% and vehicle, respectively. The computations were performed with nQuery Advisor Version 7.0 using a two-sided test with a statistical significance value of 0.05.

A sample size of 86 in the E-BPO cream, 5% and 43 in the vehicle group has 95% power to detect a statistically significant difference in the proportion of patients who have at least a 2-grade reduction at Week 12 from Baseline in IGA and are clear or almost clear. The estimated percentages with a 2-grade reduction at Week 12 from Baseline in the IGA and clear or almost clear are 53.3% and 20.0% for the E-BPO cream and vehicle, respectively.

A sample size of 200 in the E-BPO cream, 5% and 100 in the vehicle group has 95% power to detect a statistically significant difference in inflammatory lesions. The estimated absolute change from Baseline in treatment means were -14.1 and -7.4 for E-BPO cream and vehicle, respectively, with a standard deviation (SD) of 6.70 and 17.24, respectively.

The sample sizes above will be increased to give a planned enrollment of 234 in the E-BPO cream, 5% group and 117 in the vehicle group since the Phase 3 trial is expected to enroll patients who are as a group more severe than those of the Phase 2 trial. This is a consequence of some changes in the inclusion criteria.

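### A treatment-by-center interaction p-value above 0.10 cannot show that no center drives the result; leave-one-center-out should be reported in every case

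*SAP*

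**What the plan says.** SAP section 8.1.7 adds an interaction term to the primary analyses "to test for parallel treatment effect at an alpha level of 0.10". Two branches follow.

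- **p at or below 0.10:** "a sensitivity analysis that excludes analysis centers with the extreme efficacy result will be performed to determine the robustness of the treatment effect". The search is data-driven: "the process of identifying the extreme analysis centers will continue in a stepwise manner by first excluding one, then two, then three", and so on, until the interaction p-value rises above 0.10. The treatment p-value is then recomputed on the centers that remain.
- **p above 0.10:** the condition reads "if all three analyses result in interaction terms with p-values greater than 0.10". When it is met, no center is left out of any analysis, and the SAP draws this consequence: "then the conclusions from the pooled data will be considered to be free of the impact of extreme analysis centers".

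Protocol section 19.4.6 has the same rule, worded for a single test. The SAP does not define the three analyses; the shell of Table 14.2.1.1 suggests ranked ANCOVA, unranked ANCOVA and the logistic model for IGA. Neither document gives the power of the interaction test. SAP section 9 sizes the trial on the main treatment comparisons only. Under SAP section 8.7.1.1 the same p-value also decides whether the interaction stays in the primary lesion-count model.

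**The concern.** The rule turns a failure to reject into a positive finding of robustness. The trial was not sized for this test, which spreads one aberrant center over as many degrees of freedom as there are centers, less one. A lesion-count result that depends on a single center could therefore be reported as unaffected by any center, and in that branch no planned analysis removes a center to check.

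The opposite error matters too. A false signal starts a search that drops patients non-randomly and picks centers by their effect on the interaction p-value, not by their influence on the treatment estimate.

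**Working it through.** **Inputs from SAP section 9.** Planned enrollment is 234 + 117 = 351. Lesion changes are -14.1 and -7.4 (difference 6.7), with SDs 6.70 (active) and 17.24 (vehicle). IGA success is 53.3% and 20.0%. From sections 6.1 and 8.1.7: up to 28 sites, and a minimum of 10 active and 5 vehicle patients per analysis center.

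**Step 1: reproduce the plan's figures.** The SAP computes power "using a two-sided test with a statistical significance value of 0.05".

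- Lesions: "A sample size of 200 in the E-BPO cream, 5% and 100 in the vehicle group has 95% power". SE = √(6.70²/200 + 17.24²/100) = √(0.224 + 2.972) = 1.788. Then 6.7/1.788 = 3.747, and Φ(3.747 − 1.960) = 96.3% (Welch t: 96.0%), close to the stated figure.
- IGA: "A sample size of 86 in the E-BPO cream, 5% and 43 in the vehicle group has 95% power". The two-proportion formula with continuity correction gives exactly 86 and 43.

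**Step 2: number of centers K (not in the documents).** 351/28 = 12.5 patients per site, below the minimum of 15. At most 351/15 = 23 centers are possible; pairing 28 small sites would give 14. I use K = 7 to 23.

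**Step 3: power of the interaction test.** Assume equal centers, a common SD, and one center whose effect differs from the rest by D lesions:

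λ = [n₁n₀/(n₁+n₀)] × D² × (1 − 1/K) / SD²

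This is referred to a noncentral F at 0.10. Example with K = 14, SD = 11.4, D = 6.7: n₁ = 16.71 and n₀ = 8.36, so n₁n₀/(n₁+n₀) = 5.571. Then λ = 5.571 × 44.89 × (13/14) / 129.96 = 1.79, and power is 17.7%. Each cell below runs from SD 17.24 to SD 11.4.

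| D | K = 7 | K = 14 | K = 23 |
|---|---|---|---|
| 6.7 | 20–33% | 13–18% | 11–13% |
| 13.4 | 51–86% | 24–46% | 16–26% |
| 20.1 | 85–99.7% | 46–83% | 26–50% |

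A center with twice the planned effect (D = 6.7) is thus missed 67% to 89% of the time.

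**Step 4: how often the assurance would be false.** Call a result center-dependent if p ≤ 0.05 overall but p > 0.05 without the extreme center. The simulated share of such results with interaction p > 0.10, common SD, was:

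- 16 centers, one of 45 patients at 10 lesions, the rest at 2 to 3.35, SD 11.4 to 13, unranked test: about 63% to 72%.
- Equal centers, one at 13.4 and the rest at 2, SD 11.4 to 17.24: 26% to 58% (K = 8), 55% to 74% (K = 14).
- Equal centers, one at 20.1 and the rest at 2, same SDs: 1% to 25% (K = 8), 18% to 54% (K = 14).
- All three tests required to exceed 0.10 (K = 10 or 14, SD 11.4 or 13.08, assumed lesion/IGA latent correlation 0.6): 47% to 60% with one center at 10 and the rest at 2.5; 35% to 54% with one at 13.4 and the rest at 2.
- IGA alone (vehicle 20%, other centers' active rate 25%): 17% to 34% with one center at 80%; 1% to 12% with one at 95%.

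**Step 5: the SAP's own unequal SDs.** The 2:1 pooled SD is √[(2 × 6.70² + 17.24²)/3] = √129.0 = 11.4. In a center with n₀ vehicle and 2n₀ active patients, the true variance of the difference is 6.70²/(2n₀) + 17.24²/n₀ = 319.7/n₀. The model uses 129.0 × 1.5/n₀ = 193.5/n₀. The interaction mean square is therefore too large by 319.7/193.5 = 1.65 on average. In simulation the test rejects in about 59% of fully homogeneous trials with 16 centers (39% to 70% for K = 8 to 23). In the 45-patient scenario about 19% of center-dependent results are missed, partly because the test rejects so readily.

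**Step 6: how often dependence arises.** With the other centers at the planned 6.7 and one 45-patient center at 13.4, about 0.2% to 1.2% of trials depend on that center.

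**The case against.** A reader might infer that the interaction test misses most centers that drive a result. The documents do not support that in general. It holds for moderate extremes with many centers and a common SD of 11.4 or more. It fails for very extreme centers among few, for the IGA scenarios tried, and under the SAP's own SDs, where the leading problem is over-triggering.

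A reader might also infer that no planned output could reveal a dominant center. That is wrong. Tables 14.2.2.2 and 14.2.3.2 give results by arm and analysis center for both co-primaries, and section 8.1.7 plans a treatment-by-site interaction before pooling. But the robustness rule uses neither, and neither shows the treatment estimate with a center removed.

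Three further points stand:

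- The high miss rates need the other centers to show at most half the planned effect.
- Losing significance is an imperfect marker. Deleting 45 of 351 patients (13%) costs power, and with a uniform effect of 2.0 to 3.35 lesions it removes significance in 9% to 24% of significant trials that have no extreme center.
- The sentence governs interpretation, not the primary p-value, and the SAP itself acknowledges that the exclusion search is non-random and post hoc.

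**Conclusion.** The concern holds in a limited form. An interaction p-value above 0.10 does not establish that the pooled conclusions are unaffected by extreme centers, and the plan runs no center-exclusion analysis when it makes that statement. The size depends on the variance structure:

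- With a common SD of 11.4 to 13, about 16 centers and weak effects elsewhere, roughly two-thirds of center-dependent lesion results pass the unranked test. The share is lower when all three tests must pass.
- With SDs of 6.70 and 17.24, about one-fifth pass, but the test is then uninformative in the other direction.

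Either way the p-value is a poor basis for a robustness claim. Center numbers and sizes, the common SD and the extreme effects are assumptions; the documents give none of them. If the drug works as planned in the other centers, dependence on one is rare. This is a correction the sponsor should make, not a flaw in the primary test.

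**What to change.** 1. In SAP section 8.1.7, and in Protocol section 19.4.6 if it is amended, replace the sentence on freedom from extreme centers with a statement that no treatment-by-center interaction was detected at 0.10.
2. For both co-primaries, always refit the primary model leaving out one analysis center at a time, whatever the interaction p-value. Report the treatment estimates and p-values, name any center whose removal changes the conclusion, and note that some loss of significance reflects the smaller sample.
3. Define which three analyses are meant.
4. Leave the role of the interaction p-value in the primary lesion model (section 8.7.1.1) unchanged. Making it purely descriptive would conflict with that section and with the approach that SAP section 10 reports as accepted by the agency. The stepwise search can stay as a labelled sensitivity analysis.

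The cost is SAP wording and about 16 extra model fits per endpoint and imputation, with no new data or patients. The downside for the sponsor is that any dependence on one center becomes visible.

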The consistency of treatment response will be investigated across the analysis centers subsequent to combining the data as described above. Statistical tests will be conducted to identify if there are extreme analysis centers that could affect the interpretation of common statistical and clinical conclusions. An analysis center by treatment interaction will be included in the primary variable analyses to test for parallel treatment effect at an alpha level of 0.10. Change from baseline in inflammatory lesions will be analyzed with an ANCOVA (unranked or ranked) with factors of treatment, analysis center, and treatment by analysis center interaction and the respective baseline lesion count variable as a covariate. For the purpose of testing consistency of treatment response, the dichotomized IGA will be analyzed with a logistic regression procedure with factors of treatment, analysis center, and treatment by analysis center interaction. Further examination will follow for any variables that have a significant ANCOVA or logistic regression interaction term. In the event that the ANCOVA or logistic regression interaction (referred to henceforth as the "appropriate test") p-value is less than or equal to 0.10, a sensitivity analysis that excludes analysis centers with the extreme efficacy result will be performed to determine the robustness of the treatment effect. On the other hand, if the outcome of the appropriate test has a p-value greater than 0.10, then the conclusions from the pooled data will be considered to be free of the impact of extreme analysis centers.

The first step in conducting a sensitivity analysis is to identify the extreme analysis center or centers that contribute to the statistical significance of the appropriate test. The process involves submitting subsets of analysis centers to the appropriate test and observing the appropriate test p-value for the subset. Subsets with p-values greater than 0.10 for the appropriate test are considered homogeneous.

The search for an extreme analysis center begins by analyzing all subsets that can be created by excluding one analysis center. If one or more of the subsets result in an appropriate test p-value greater than or equal to 0.10, then the analysis center excluded from the subset with the largest p-value for the appropriate test is deemed to be the extreme analysis center.

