treatment-by-analysis center interaction p-value is ≤ 0.10 , the interaction will also be included in the model). The residuals from the unranked analysis will be used to calculate the skewness p-value. The skewness p-value will determine which analysis results to report:

- i. Skewness p-value > 0.01 : Report results from the parametric (unranked) ANCOVA.
 - ii. Skewness p-value ≤ 0.01 : Report results from the non-parametric (ranked) ANCOVA.
4. If there was a significant treatment by analysis center interaction (as determined in step 1 – the pooling analysis), a sensitivity analysis will be performed as described in Section 8.1.7 to find the extreme analysis center(s). Then step 3 above will be repeated the extreme analysis center(s) removed, to confirm the treatment response.

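### The search for extreme centers ignores the direction of their effect, so a rerun that has dropped an unfavourable center cannot be read as confirming the treatment response

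*SAP*

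**What the plan says.** SAP 8.1.7 includes a treatment-by-analysis-center interaction in the primary analyses "to test for parallel treatment effect at an alpha level of 0.10". If that p-value is 0.10 or less, a search begins. Protocol 19.4.6 gives its purpose: "a sensitivity analysis that excludes analysis centers with the extreme efficacy result will be performed to determine the robustness of the treatment effect".

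The search deletes each analysis center in turn and recomputes the interaction p-value. The choice is then made on that p-value alone: "the analysis center excluded from the subset with the largest p-values for the appropriate test is deemed to be the extreme analysis center". If one deletion is not enough, it continues "by first excluding one, then two, then three, etc., analysis centers until the appropriate test p-value exceeds 0.10".

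The result is used in two places. SAP 8.1.7 says: "Inferences will be drawn from the p-values as well as any pertinent observations regarding the extreme analysis center or centers". For lesion counts, SAP 8.7.1.1 step 4 adds: "Then step 3 above will be repeated the extreme analysis center(s) removed, to confirm the treatment response".

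SAP 8.1.7 states without condition that the exclusion is non-random and that its effect on power cannot be predicted. The explicit post-hoc caution is conditional: "In the event that the treatment effect of the remaining subset is not statistically significant, due consideration of the post-hoc aspects of the process" is to be given when results are interpreted. No matching sentence covers a remaining subset that is significant.

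**The concern.** A robustness check is informative only if it could have gone the other way. Here the center to drop is chosen by how much it disturbs homogeneity. Whether it pulled the pooled effect up or down is not considered.

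If the center removed was one where vehicle did relatively well, the remaining estimate rises and a significant result stays significant almost automatically. The step 4 wording would still present that rerun as confirmation. The one explicit post-hoc caution would not apply, because the rerun is significant.

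What is at stake is the robustness statement in the trial report, in exactly the situation where centers disagree. The primary decision is not at stake.

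**Working it through.** **Inputs from the documents.** Interaction level 0.10 (SAP 8.1.7). Treatment test two-sided 0.05 (SAP 8.1). Planned 234 active and 117 vehicle; lesion-count means -14.1 and -7.4, SDs 6.70 and 17.24 (SAP 9). Up to 28 sites (SAP 6.1). Minimum analysis-center size 15 (SAP 8.1.7), so at most 351/15 = 23.4, that is 23 centers. The number of analysis centers is not given, and no error rate is stated for the search.

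**The plan's own figures.** For lesion counts at 200/100, SE = sqrt(6.70²/200 + 17.24²/100) = sqrt(0.2245 + 2.9722) = 1.788. Then 6.7/1.788 - 1.96 = 1.79, which is 96.3% power against 95% stated. IGA gives 43 in vehicle with continuity correction, as stated. In simulation with homogeneous centers the interaction test fires in 10.0% of trials, its nominal level.

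**Why direction decides the outcome.** Take K equal centers, pooled estimate d with standard error s, and treat the residual variance as known. Removing center j gives

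- estimate: d + (d - d_j)/(K - 1)
- standard error: s × sqrt(K/(K - 1))

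With K = 14 (an assumption), sqrt(14/13) = 1.038. A single center's standard error is sqrt(14) = 3.74 s. As an illustration, let the removed center lie two of its own standard errors, 7.48 s, from the pooled effect. The estimate moves by 7.48/13 = 0.576 s.

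- Unfavourable center removed, starting from z = 1.96: (1.96 + 0.576)/1.038 = 2.44. Significance is kept, even from the borderline.
- Favourable center removed, starting from z = 1.96: (1.96 - 0.576)/1.038 = 1.33. Significance is lost. To survive, the starting z must be at least 1.96 × 1.038 + 0.576 = 2.61.

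**Simulation of the rule.** The design was 2:1 allocation with about 351 patients, normal errors with a common SD, an F-test for interaction at 0.10, the search over one and then more deletions, and then the treatment test on the remainder. Baseline covariate and imputation were omitted. With no true effect and a common SD, the size of that SD is only a scale and does not affect these rates. Among trials with a chance result for active and interaction p ≤ 0.10:

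| Runs (lesion counts, no true effect, no outlier) | Centers assumed | Chance findings confirmed |
|---|---|---|
| Set 1 | 5 / 8 / 10 | 49% / 55-56% / 52% |
| Set 1 | 12 / 16 / 23 | 53-56% / 57-58% / 58% |
| Set 2 | 6 / 10 / 14 / 20 | 53% / 53% / 56% / 60% |
| Set 3 | 6 to 14 | 52-55% |
| Set 4 | 14 | 59% |

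- The removed center was less favourable than the pooled effect in 50-51% of searches in set 1. Among the chance findings, deletion enlarged the effect in 49-53% (sets 2 and 4).
- When deletion enlarged the effect, 99.5% or more were confirmed. When a favourable center went, or the effect shrank, 1-19% were confirmed across runs.
- Requiring every leave-one-center-out analysis to stay significant would have confirmed 4%, 11%, 16% and 23% with 6, 10, 14 and 20 centers.
- With one favourable outlying center and no effect elsewhere, the search confirmed 13% (12 centers, outlier +1.5 SD), 16% and 22% in separate runs.

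These situations are rare under no effect: 0.10 × 0.025 = 0.25% of trials, matching 975 of 400,000 (0.24%) in set 4.

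For IGA, with Breslow-Day and Cochran-Mantel-Haenszel tests standing in for the logistic models and assumed success rates of 0.20 or 0.35, 66-85% of chance findings were confirmed. This is only indicative.

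**The case against.** The strongest reply has four parts.

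1. **It is only a sensitivity analysis.** Nothing is removed from the primary test, and SAP 8.1.8 gates the secondary endpoints on the co-primary results. This stands. A reader might infer that the search inflates the trial's type I error; the documents give no support for that.

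2. **The rule does not favour the product.** Being blind to direction, it is symmetric, and where a favourable center drives the result it removes that center and usually withdraws the support. This stands too. A reader might infer that the search confirms most false positives. For lesion counts the figure is about half, and a minority with 5 centers. The clear majority appears only for IGA, under approximate tests. The documents fix neither the number of centers nor any operating characteristic that would support a stronger statement.

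3. **Direction will be visible anyway.** Planned Tables 14.2.2.2 and 14.2.3.2 show both co-primaries by arm and center, and SAP 8.1.7 allows pertinent observations on the extreme center. This stands in part. The tables give no leave-one-center-out treatment estimate, and nothing obliges the report to state direction or to withhold the word confirm.

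4. **A worst-case leave-one-out rule is too strict.** With an effect of 5 lesions in 13 centers and -8 in one, the average is (13 × 5 - 8)/14 = 4.1, so the product works overall. At SD 15 the search confirmed 87-90% and the worst leave-one-out 56-63%. At the SAP 9 difference of 6.7 and the pooled SD sqrt((199 × 6.70² + 99 × 17.24²)/298) = 11.35, the figures were 99% and about 97%. This stands. Leave-one-out results should therefore be added, without making the worst one the sole criterion.

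**Conclusion.** The point holds in limited form. A rerun after removing a less favourable center is not evidence of robustness, because a significant result almost always stays significant (99.5% or more in simulation). Without a true effect or an outlying center, that branch arises about half the time, and 49-60% of chance lesion-count findings are confirmed. The rule does its job when a single favourable center is responsible (about 13-22% confirmed). The disclosure of non-random exclusion does not mention direction, and the post-hoc caution covers only one of the two outcomes.

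The percentages rest on assumed numbers and sizes of centers, normal errors with a common SD (SAP 9 plans for unequal SDs), and no covariate or imputation. The scenarios with a true effect or an outlying center also depend on the assumed SD and effect sizes. The dependence on direction follows from the algebra and does not rest on those choices. The consequence is confined to what the report may claim about robustness.

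**What to change.** In SAP 8.1.7, SAP 8.7.1.1 step 4 and Protocol 19.4.6, when the interaction p-value is 0.10 or less:

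- in addition to the search, report the treatment estimate, 95% CI and p-value with each analysis center left out in turn, and point out the least favourable;
- state whether each center removed by the search was more or less favourable than the pooled effect;
- do not describe the rerun as confirming the treatment response when the removed center was less favourable;
- apply the post-hoc caution to significant and non-significant reruns alike.

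The cost is SAP and protocol wording plus about one extra model fit per center for each co-primary endpoint. The robustness statement will sometimes be less favourable, including for some real effects.
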